6.4 Quality Control

Quality controls employed will be outlined in the final observational study report.

6.5 Database Retention and Archiving of Study Documents

Location of database and supporting documentation will be outlined in the final observational study report.

6.6 Registration of Study on Public Website

This study will be registered on the European Network of Centres for Pharmacoepidemiology and Pharmacovigilance (ENCePP).

7 ADVERSE EVENT REPORTING

This study does not meet the criteria for adverse event reporting.

8 GLOSSARY OF TERMS AND LIST OF ABBREVIATIONS

8.1 Glossary of Terms

Not applicable.

8.2 List of Abbreviations

Term	Definition
ATC	Anatomic Therapeutic Chemical
СНМР	Committee for Medicinal Products for Human Use
CIAP	International Classification of Primary Care
eGFR	Estimated Glomerular Filtration Rate
EU	Europe
GEP	Good Epidemiology Practices
ICD-9	International Classification of Diseases, 9 th edition
ICD-10	International Classification of Diseases, 10 th edition
ISPE	International Society for Pharmacoepidemiology
OAD	Oral Antidiabetic Drug
SAP	Statistical Analysis Plan
SGLT-2	Sodium glucose co-transporter
SmPC	Summary of Product Characteristics
T2DM	Type 2 Diabetes Mellitus

Date: 13-Nov-2013 24

APPENDIX 1 CSD DATA CAPTURE SYSTEM (PHYSICIAN SOFTWARE)

A Software package is installed in the physician's office for patient file follow-up and practice management.

The package includes the computer, software (see table below) Internet access, national health insurance institution transfer system, additional documentation (free drug prescription database). Also offered to participating physicians: training at no cost, priority in information system support (computer, Internet, software hotline), newsletter and a possible recruitment proposal in clinical trials or observational surveys.

Complete computerized clinical records are gathered in the Electronic Medical Records (EMR).

	Software for Physicians	CEGEDIM Software Company / Preferred Partners		
BELGIUM	Heallth ^{one}	HDMP		
FRANCE	Doc'Ware®	CEGEDIM Logiciels Médicaux		
GERMANY	Software "Albis on Windows® aSoftware TurboMed® MCS-ISYNET ® DOCconcept®	CompuGROUP Holding MCS AG DOCexpert		
ITALY	Millewin®	Millenium		
UNITED KINGDOM	Vision®	In Practice Systems		
SPAIN	OMI-AF®	Stacks		

The data are uploaded by modem on a regular basis with a simple validation green light provided by the physician.

Once the MD has accepted to upload the data, they are transmitted to CSD every time the MD provides the agreed signal in Belgium, France, Italy, UK and Spain, whereas in Germany the transmission to CSD occurs twice a month.

The most recent data collected from CSD Databases can be viewed daily in Belgium, France, Italy, UK and Spain, and biweekly in Germany; providing a high level of quality of information.

Data collected are voluntarily recorded by the General Practitioner in his usual routine practice into the patient EMR. Since data are collected directly by the physicians and uploaded in an anonymized way, it is not possible to refer back to patients' files and perform any site quality control or any modification by asking more detailed information on any points that our client would like to know more about.

APPENDIX 2 KEY DATA METRICS OF THE GP'S LPD

		France	ITALY	UK	GERMANY	SPAIN	BELGIUM		
GENERAL DATA									
Number of patients having visited a physician		100,0%	100,0%	100,0%	100,0%	100,00%	100,00%		
Of which	Male	46,5%	46,7%	46,9%	45,9%	43,4%	46,4%		
	Female	53,5%	53,3%	53,1%	54,1%	56,6%	53,6%		
	Average age (years)	38,5 yo	50,2 yo	40,8 yo	49,2 yo	52,3 yo	42,8 yo		
BIOMETRIC DA	ATA								
Number of patients with a weight recorded (1 year history)		39,9%	15,1%	28,2%	15,3%	16,5%	14,4%		
Number of patients with height recorded (1 year history)		20,0%	14,9%	13,9%	15,1%	12,9%	6,8%		
Number of patients with BMI recorded (1 year history)		19,2%	14,8%	12,8%	14,9%	12,2%	6,5%		
Number of patients with BMI recorded (3 years history + calc)		32,2%	30,7%	30,1%	17,4%	30,1%	12,0%		
Number of patients with waist recorded (1 year history)		0,3%		0,2%					
Number of patients with Blood Pressure recorded (1 year history)		33,4%	26,9%	38,9%	14,6%	25,0%	35,3%		
	average records by year by patient	2,63	2,13	2,04	4,10	1,76	2,80		
BIOLOGICAL EXAMS									
Number of patients with a fasting blood glucose test		7,8%	39,4%	20,9%	32,7%	27,3%	35,1%		
Number of patients with a Hba1c rate		2,7%	11,3%	8,9%	44,5%	6,3%	7,7%		
Number of patients with Total cholesterol		7,3%	33,4%	23,7%	34,8%	0,0%	27,4%		
Number of patients with LDL		6,9%	27,7%	15,7%	27,8%	14,6%	24,8%		
Number of patients with HDL		6,8%	29,3%	20,5%	26,0%	19,5%	26,1%		
Number of patients with Triglyceride		7,3%	32,0%	17,3%	30,5%	22,8%	26,4%		
Number of patients with Transaminases SGOT (ASAT)		4,9%	26,5%	4,3%	22,4%	13,0%	29,0%		
Number of patients with Transaminases SGPT (ALAT)		5,0%	29,8%	31,2%	30,1%	18,5%	31,1%		
Number of patients with Gamma-GT		3,0%	17,7%	11,2%	38,4%	20,3%	28,7%		

APPENDIX 3 CODE LISTS

	ICD9	ICD10
T2DM	250.x0	E10.x
Acute renal failure	584.x	N17.x
Severe chronic renal failure	585.x	N18.3, N18.4, N18.5
U failure	586.x	N19.
Dialysis	V45.11, V56.x	Y84.1
Renal transplantation	E878.0	Y83.0
Congestive heart failure	428.0	150.0
Hypertension	401.x	I10.x, I11.x, I12.x, I13.x, I15.x

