Page: 1

Protocol Number: MB102134

Date: 13-Nov-2013

Observational Study Protocol MB102134

OBSERVATIONAL SINGLE-COHORT DATA BASE STUDY OF DAPAGLIFLOZIN UTILISATION IN EUROPE

This document is the confidential and proprietary information of Bristol-Myers Squibb Company, its global affiliates (BMS) and AstraZeneca (AZ). By reviewing this document, you agree to keep it confidential and to use and disclose it solely for the purpose of assessing whether your organization will participate in and/or the performance of the proposed BMS/AZ-sponsored study. Any permitted disclosures will be made only on a confidential "need to know" basis within your organization or to your independent ethics committee(s). Any other use, copying, disclosure or dissemination of this information is strictly prohibited unless expressly authorized in writing by BMS/AZ. Any supplemental information (e.g., amendments) that may be added to this document is also confidential and proprietary to BMS/AZ and must be kept in confidence in the same manner as the contents of this document. Any person who receives this document without due authorization from BMS/AZ is requested to return it to BMS/AZ or promptly destroy it. All other rights reserved.

SYNOPSIS

Observational Study Protocol MB102134

Protocol Title: Observational Single-Cohort Data Base Study of Dapagliflozin Utilisation in Europe

Department: Bristol-Myers Squibb Epidemiology and AstraZeneca Global Epidemiology

Objective(s): *Primary objective:* To describe the characteristics of European patients newly prescribed dapagliflozin by age, sex, dapagliflozin dose, country, selected co-morbidities, and selected concomitant medications.

The proposed drug utilization study will specifically describe dapagliflozin use in:

- patients > 75 years-old,
- combination use with loop diuretics or pioglitazone,
- patients with a known history of moderate or severe renal impairment and in kidney failure,
- patients lacking a diagnostic code indicating type 2 diabetes.

Study Design: This is an observational single-cohort data base study with descriptive data analyses among patients receiving dapagliflozin within electronic medical records in Europe. The study will describe the utilization pattern of dapagliflozin during the first 3.5 years after marketing authorization and launch in Europe specifically in Belgium, France, Germany, Italy, Spain and United Kingdom.

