1 INTRODUCTION

Dapagliflozin (BMS-512148) is a highly potent, selective, and reversible inhibitor of the human renal sodium glucose co-transporter (SGLT2), the major transporter responsible for renal glucose reabsorption. Dapagliflozin lowers plasma glucose by inhibiting the renal reabsorption of glucose, and by promoting its urinary excretion making it a member of an emerging therapeutic class in the treatment of type 2 diabetes mellitus (T2DM).

Dapagliflozin is indicated in adults aged 18 years and older with type 2 diabetes mellitus (T2DM) to improve glycaemic control as:

- Monotherapy when diet and exercise alone do not provide adequate glycaemic control in patients for whom metformin is considered inappropriate due to intolerance.
- Add-on combination therapy in combination with other glucose lowering medicinal products including insulin, when these, together with diet and exercise, do not provide adequate glycaemic control.

According to the summary of product characteristics (SmPC), the recommended posology and method of administration are the following:

- The recommended dose is 10 mg dapagliflozin once daily for monotherapy and add-on combination therapy with other glucose lowering medications including insulin. When dapagliflozin is used in combination with insulin or an insulin secretagogue, such as a sulphonylurea, a lower dose of insulin or insulin secretagogue may be considered to reduce the risk of hypoglycaemia.
- Dapagliflozin can be taken orally once daily at any time of day with or without food. Tablets are to be swallowed whole.

The following precautions for use must be taken for the following special populations:

- Renal impairment: The efficacy of dapagliflozin is dependent on renal function, and efficacy is reduced in patients who have moderate renal impairment and likely absent in patients with severe renal impairment. Dapagliflozin is not recommended for use in patients with moderate to severe renal impairment (patients with creatinine clearance [CrCl] < 60 ml/min or estimated glomerular filtration rate [eGFR] < 60 ml/min/1.73 m²). No dosage adjustment is indicated in patients with mild renal impairment.
- Hepatic impairment: No dosage adjustment is necessary for patients with mild or moderate hepatic impairment. In patients with severe hepatic impairment, a starting dose of 5 mg is recommended. If well tolerated, the dose may be increased to 10 mg.

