1.2 Research Question

Research question 1: What are the baseline characteristics of the patients prescribed dapagliflozin in Europe?

Research question 2: What proportion of patients prescribed dapagliflozin have baseline moderate to severe renal impairment?

Research question 3: What proportion of patients prescribed dapagliflozin are 75 years of age or older at the time of the index prescription?

Research question 4: What proportion of patients prescribed dapagliflozin are also users of loop diuretics or pioglitazone during the baseline period and the available follow-up period?

Research Question 5: What proportion of patients prescribed dapagliflozin does not have a diagnosis of Type II Diabetes during the baseline period or on the index date?

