3.4.1 Outcomes/Endpoint Variables

Table 3.4.1-1 includes the characteristics and definitions of how dapagliflozin users will be categorized and described.

Table 3.4.1-1: Categorization of Dapagliflozin Users

Characteristic	Definition
Patient Demographics, at initiation of dapagliflozin use:	
Age categories	< 45, 45-59, 60-74, >= 75
Sex	Male or Female
Country	Belgium, France, Germany, Italy, Spain, United Kingdom
Concomitant medications before, at initiation of and	Loop diuretics (ATC code C03Cx)
during dapagliflozin use 1	Pioglitazone (Actos, Glustin) (ATC code A10BG),
	Biguanides (ATC Code A10BA)
	Sulfonamide derivates (ATC code A10BB and A10BC)
	Dipeptidyl peptidase 4 inhibitors (DDP4) (ATC code A10BH)
	Glucagon-like peptide 1 (GLP-1, exenatide, liraglutide, ATC code A10BX),
	Alpha glucosidase inhibitors (ATC code A10BF).
	Insulin (ATC code A10A)
Concomitant co-morbidities, at initiation of dapagliflozin use:	
Baseline history of moderate renal impairment	CrCl or eGFR ² value between 30-60 within 12 months prior to the dapagliflozin dispensing
Baseline history of severe renal impairment	CrCl or eGFR value < 30 within 12 months prior to the dapagliflozin dispensing
Baseline history of renal failure	Diagnosis codes for end stage renal disease or dialysis (see Appendix 3)
Congestive heart failure	Diagnosis codes for congestive heart failure (see Appendix 3)
Hypertension	Diagnosis codes for hypertension (see Appendix 3)
Type 2 Diabetes Mellitus, at initiation of dapagliflozin use:	Diagnostic code for T2DM within 12 months prior to the dapagliflozin dispensing (see Appendix 3) OR
	Prescription for an antiglycemic medication within 12 months prior to the dapagliflozin dispensing

Table 3.4.1-1: Categorization of Dapagliflozin Users

Characteristic	Definition
Dapagliflozin Dose, at initiation of dapagliflozin	10 mg
use:	5 mg
Off-Label Use	Patients meeting one of the following criteria:
	 17 years old or younger on index date
	• 75 years of age or older on index date
	 No diagnostic codes for Type 2 Diabetes Mellitus, at or before the initiation of dapagliflozin use (see definition above)
	• Baseline history of moderate renal impairment (see definition above)
	• Baseline history of severe renal impairment (see definition above)
	• Baseline history of renal failure (see definition above)

^[1] Pioglitazone sales are suspended in France and Germany

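### Appendix 3 lists ICD-10 E10.x, the type 1 category, as the code for T2DM, so German type 2 initiators whom only a diagnosis code could identify are counted as having no T2DM

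*Protocol*

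**What the plan says.** Appendix 3 has a single diabetes row: "T2DM 250.x0 E10.x", the first code under ICD-9 and the second under ICD-10. No other section adds to or corrects it.

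The row feeds one of the four subgroups named in the primary objective, and that subgroup is described in different ways:

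- The synopsis names "patients lacking a diagnostic code indicating type 2 diabetes".
- Section 1.2, research question 5, asks for the proportion of patients prescribed the drug that "does not have a diagnosis of Type II Diabetes during the baseline period or on the index date".
- Table 3.4.1-1 defines T2DM by two alternatives. The first is "Diagnostic code for T2DM within 12 months prior to the dapagliflozin dispensing (see Appendix 3) OR". The second, which that last word joins to it, is "Prescription for an antiglycemic medication within 12 months prior to the dapagliflozin dispensing".
- The off-label row of the same table reads "No diagnostic codes for Type 2 Diabetes Mellitus, at or before the initiation of dapagliflozin use (see definition above"). It speaks of codes only, yet points back to the two-part definition.

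Table 3.3.1-1 shows Germany coding diagnoses in ICD-10, Italy in ICD-9, Spain in CIAP mapped to ICD-9, and the UK in Read codes.

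**The concern.** E10 is the wrong disease category. The meaning of the codes is not spelled out in the protocol, but it is fixed by the classifications that the protocol adopts: E10 is type 1 and E11 is type 2. In ICD-9 the fifth digit 0 is type II or unspecified, not stated as uncontrolled, and the fifth digit 2 is type II, uncontrolled. So the ICD-10 entry names another disease and the ICD-9 entry covers only part of the right one.

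Use in patients without T2DM is something this study must report, on regulatory request and to the CHMP (Sections 1.1 and 4.3). With the list as printed, a German patient treated within the indication can be counted as outside it, and a type 1 patient, who is outside it, is counted as inside. Differences between Germany and the other countries would then partly reflect the code list and not prescribing.

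**Working it through.** **The plan's own scale.** Table 4.2-1 for Germany: 70,000 × 55.3% = 38,710 users of oral antidiabetics. With the 2013 uptake of 1.0% in Table 4.2-2 this gives 387.1, matching the stated 387. Over 2012-2017 the uptakes sum to 0.2 + 1.0 + 1.4 + 1.9 + 2.5 + 3.0 = 10.0%, giving 3,871, as stated (19.0% of 20,325). I use 387 as the scale, because Section 1.1 says that Germany reimbursed the drug only for 2013 and because the forecast runs past the 42-month analysis.

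**Inputs the documents do not give (assumed ranges).**

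- e = share of German initiators with an E10 code: 1-5%
- u = share that truly lacks a type 2 code: 2-10%
- r = share with an antiglycaemic prescription in the prior 12 months: 70-95%, taken as unrelated to the code

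**Germany, code only** (synopsis and research question 5 as worded).

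- Reported without T2DM, list as printed: 1 − e = 95-99%, or 368-383 of 387.
- With the type 2 category: u = 2-10%.

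**Germany, code or prescription** (Table 3.4.1-1). A patient is reported without T2DM only if both arms fail: (1 − e)(1 − r) with the list as printed, u(1 − r) with the type 2 category.

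| r | E10.x as printed | of 387 | type 2 category |
|---|---|---|---|
| 70% | 28.5-29.7% | 110-115 | 0.6-3.0% |
| 90% | 9.5-9.9% | 37-38 | 0.2-1.0% |
| 95% | 4.75-4.95% | 18-19 | 0.1-0.5% |

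So about 5-30% would be reported as without T2DM, against 0.1-3% with the right category. Almost all of the reported group is an artefact of the code. It consists of initiators with no recorded earlier antiglycaemic prescription, for whom the code alone decides. Patients starting under the monotherapy indication (Section 1) can fall here, as can those whose earlier drugs came from specialists, whose prescriptions the databases do not capture (Section 5.2).

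**Type 1 patients.** As printed, an E10 code makes them T2DM. After a change to E11.x, a type 1 patient with insulin in the prior 12 months still becomes T2DM through the prescription arm, which is not limited to any class of antiglycaemic drug. Correcting the code alone does not make this group visible.

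**Italy and Spain (ICD-9), code only.** If q is the share of T2DM patients whose only code in the window is 250.x2, the reported share is u + (1 − u)q. At u = 5%, each percentage point of q adds 0.95 points. At q = 0 nothing is added. The documents give no value for q.

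**The case against.** The strongest counter-argument is the prescription arm. A reader who stops at the word OR in Table 3.4.1-1 might infer that the T2DM classification in Germany is simply inverted, with about 100% of type 2 initiators misclassified. The table does not support that: a previously treated type 2 patient qualifies whichever code is listed, and add-on use is one of the two labelled uses. The inversion holds only on the code-only wording of research question 5 and the synopsis. This part of the objection stands.

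A reader might also infer that the result is inflated in the ICD-9 databases. The omission of 250.x2 is plain on the face of the list, and the indication covers add-on use "when these, together with diet and exercise, do not provide adequate glycaemic control". But nothing in the protocol shows that GPs record this with the uncontrolled fifth digit. Patients may also carry a 250.x0 code, the unspecified type within 250.x0 pulls the other way, and the Spanish mapping is not given. Only a possible gap of unknown size remains.

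Reach is limited too. The UK uses Read codes, for which Appendix 3 has no column, and the mapping for Belgium and France cannot be read in the text at hand.

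Two further defences do not succeed. Section 3.3.1 leaves harmonisation algorithms to the SAP, but Appendix 3 already fixes the codes, and Section 4.1 says that the SAP elaborates on the protocol and that major modifications need an amendment. A misread digit in the PDF is possible, since the heart-failure code in the same table appears to have lost a letter. Yet the other ICD-10 entries, such as N17.x and I10.x, read as expected. A look at the source page settles it.

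**Conclusion.** Wrong as written, and to be corrected before the first extraction. The ICD-10 entry for T2DM is the type 1 category, and it enters a named subgroup of the primary objective and the off-label criterion. The effect is established for Germany only. It reaches nearly all type 2 initiators on the code-only wording (95-99% reported without T2DM if 1-5% carry an E10 code). Under Table 3.4.1-1 it produces about 5-30% reported without T2DM if 70-95% were previously treated. These shares are assumptions; the direction of the error does not depend on them.

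The gap between the two figures shows a second defect: the protocol does not settle whether a prescription can stand in for a diagnosis code. The ICD-9 entry may be incomplete, with an effect that could be zero.

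**What to change.** 1. In the T2DM row of Appendix 3, replace E10.x with E11.x and extend 250.x0 to 250.x0 plus 250.x2.
2. State one definition for research question 5 and the off-label row. Report the code-only result, which matches the wording of research question 5 and the synopsis, and show the code-or-prescription result separately.
3. Add a type 1 row (ICD-10 E10.x; ICD-9 250.x1 and 250.x3). Report initiators with only a type 1 code as their own group, regardless of the prescription arm, because prior insulin would otherwise count them as T2DM.

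The cost is small: edits to Appendix 3 and Table 3.4.1-1 by amendment before the first extraction, and a few more lines in the output tables. No new data are needed.

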3.3.1 Content of the Cegedim LPDs

Data are entered during usual patient care and submitted daily to the Cegedim coordinating center, cleaned and de-identified and then made available in the LPDs for research no later than one month after submission. The following anonymized patient data collected from GPs' practice will be extracted from the databases:

- Demographics (Year of birth, gender, registration dates),
- Medical History (Event dates, diagnosis, symptoms, risk factors, co-morbidities, referrals,
- Treatments (indication, molecule/brand, dosage, posology, date and length of prescription),
- Clinical Data (Height, weight, BP, life habits),
- Clinical laboratory tests, X-ray and other investigations (not available in Germany).

The median follow-up duration of a patient in the data base is 27 months in Germany, 36 months in France, 44 months in Spain, 46 months in Belgium, 112 months in Italy and 117 months in UK.

Patient data collected by Cegedim in each country participating in the LPD varies to some extent to accommodate local needs. However, all countries collect data on medical co-morbidities and outcomes, prescriptions, demographics, and physician characteristics. Key metrics of the GPs' LPDs are provided for each country in Appendix 2 (2012 data).

In the LPDs, diagnoses of clinical events are recorded as diagnostic codes (*e.g.* ICD-9, READ). These codes from the different participating countries will be harmonized based on pre-specified algorithms developed prior to the analysis and listed in the statistical analytic plan. Table 3.3.1-1 summarizes the coding conventions for each of the databases.

Table 3.3.1-1: Data Coding Conventions in the Different Countries

	Belgium	France	UK	Italy	Germany	Spain
Drug code dictionary	Association Pharmacologique Belge	Claude Bernard	Multilex	Farmadati	Abdata	Vademecum
Therapy classification	European Pharmaceutical Marketing Research Association (EphMRA)		British National Formulary (BNF)	ATC	ATC	ATC
Disease classification	Cegedim prop thesaurus (mapped	-	Read Codes	ICD-9	ICD-10	CIAP mapped to ICD-9

ATC = Anatomic, Therapeutic, Chemical

ICD = International Classification of Disease

CIAP = International Classification of Primary Care

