3.3.2 Content of the Cegedim LPDs for T2DM patients

Table 3.3.2-1 gives approximate estimates of the proportion of T2DM patients captured using the Cegedim LPD in each country.

The total number of T2DM patients in the respective countries during the same period is not known, but may be roughly estimated based on information from the Diabetes Atlas 2012¹ and assuming that this population represents approximately 90 % of the total diabetic population.

Table 3.3.2-1: Estimates of the proportion of T2DM patients captured in Cegedim LPDs (year 2012)

	Source	France	Germany	Italy	Spain	Belgium	UK
Diabetic Population (in thousands)	Diabetes Atlas http://www.idf.org/diabetesatlas	3,493	5,249	3,903	3,249	547	3,336
Estimates of T2DM patients Total Population (in thousands)	0.9 x Diabetic population	3,115	4,724	3,523	2,925	493	3,002
T2DM patients in CegedimLPD s (in thousands)	Cegedim LPD	65	37	42	14	13	118
% of T2DM population in Cegedim LPDs:	T2DM patients in Cegedim LPDs/Estimates of T2DM patients Total Population	2.1%	0.8%	1.2%	0.5%	2.6%	3.9%

Date: 13-Nov-2013

Key metrics for the T2DM patients in GP's LPDs are provided for each country in Table 3.3.2-2.

Information collected during the course of one year (2012), on serum creatinine and eGFR for T2DM patients is detailed in Table 3.3.2-3.

These data, when insufficiently documented in the course of one year, can be extracted over an extended period of time (two years) in patients' medical record in order to add information and increase possibilities for meaningful analyses.

In addition, this information can be complemented in each country by a search of patient's medical records with a list of diagnostic codes identifying chronic kidney disease, renal failure, end-stage renal disease and related diagnoses (according to Wan J. et al² and Denburg M.R., et al³.)

Table 3.3.2-2: Key Data Metrics of T2DM Patients in GP's LPDs

	France	ITALY	UK	GERMANY	SPAIN	BELGIUM
GENERAL DATA						
Number of patients having visited a physician	100,00%	100,00%	100,00%	100,00%	100,00%	100,00%
Of which Male	58,0%	51,9%	55,2%	51,8%	53,8%	53,4%
Female	42,0%	48,1%	44,8%	48,2%	46,2%	46,6%
BIOMETRIC DATA	19					
Number of patients with a weight recorded (1 year history)	56,0%	39,9%	83,5%	29,1%	28,3%	37,3%
Number of patients with height recorded (1 year history)	20,6%	39,6%	30,8%	28,3%	23,2%	13,9%
Number of patients with BMI recorded (1 year history)	20,2%	39,4%	29,0%	28,2%	20,7%	13,2%

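### Renal failure is defined by end-stage codes in Appendix 3, but Appendix 3 has no end-stage row, and its one chronic kidney row differs in scope between ICD-9 and ICD-10

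*Protocol*

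**What the plan says.** Protocol section 3.4.1, Table 3.4.1-1, sets three renal categories at initiation of dapagliflozin:

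- **Moderate impairment:** a CrCl or eGFR "value between 30-60 within 12 months prior to the dapagliflozin dispensing".
- **Severe impairment:** "CrCl or eGFR value < 30 within 12 months prior to the dapagliflozin dispensing".
- **Renal failure:** "Diagnosis codes for end stage renal disease or dialysis (see Appendix 3"). This category has no laboratory route.

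The same table makes each of the three a criterion for off-label use. Section 2.1 asks for a separate analysis of the renal subgroup and names all three in one bullet.

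The kidney rows of Appendix 3 are:

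| Row | ICD-9 | ICD-10 |
|---|---|---|
| Acute failure | 584.x | N17.x |
| "Severe chronic renal failure" | 585.x | "N18.3, N18.4, N18.5" |
| A further failure row (label partly lost in the copy at hand) | 586.x | N19 |
| Dialysis | V45.11, V56.x | Y84.1 |
| Renal transplantation | E878.0 | Y83.0 |

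Two other statements bear on the point. Section 3.3.2 says of creatinine and eGFR that "this information can be complemented in each country by a search of patient's medical records with a list of diagnostic codes". Section 3.3.1 says of diagnostic codes: "These codes from the different participating countries will be harmonized based on pre-specified algorithms developed prior to the analysis", with the algorithms to be listed in the SAP.

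**The concern.** Renal failure is the one renal category that rests wholly on the code list, and the list does not contain the category it is cited for. An analyst must choose which rows to use, and the protocol gives no rule for choosing. The one chronic row also mixes the protocol's own bands, and its ICD-9 and ICD-10 cells do not select the same patients.

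At stake is the separate count of patients with renal failure, in a study done at a regulator's request under the Risk Management Plan (section 1.1). A difference between countries in that count could come from the code list alone.

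**Working it through.** The protocol states no renal-failure count, so there is no figure to reproduce. The check sets the definitions beside the code list.

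**1. The cross-reference.** Table 3.4.1-1 needs end-stage disease or dialysis. Appendix 3 has a dialysis row and no end-stage row. By the classifications, end-stage disease falls inside 585.x and N18.5, but the chronic row does not separate it from earlier stages.

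**2. The label against the bands.** The chronic row is labelled severe. Table 3.4.1-1 puts severe below 30 and moderate at 30-60. N18.3 is stage 3 in ICD-10, so a moderate-band code sits under a severe label.

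**3. The two columns.** Among all users, let *m* be the share coded with stage 1-2 or unstaged chronic kidney disease, *s3* and *s4* the shares coded at stages 3 and 4, and *e* the share coded at stage 5 or end-stage. The chronic row then returns:

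- ICD-10: *s3 + s4 + e*, an excess over *e* of *s3 + s4*.
- ICD-9: *m + s3 + s4 + e*, an excess over *e* of *m + s3 + s4*.
- ICD-9 minus ICD-10, for the same patients: *m*.

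None of these terms can be negative, so the direction is fixed: both columns over-count, and ICD-9 over-counts by more whenever *m* is above zero. The documents give none of the four shares. If instead only the dialysis row is used, the count omits the part of *e* that is not on dialysis. Neither choice yields the defined category.

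**4. Countries.** Table 3.3.1-1 gives ICD-9 for Italy, a mapping to ICD-9 for Spain, ICD-10 for Germany, Read codes for the UK and a proprietary thesaurus for Belgium and France. The forecast totals in Table 4.2-1, used only as relative weights, give:

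| Coding | Forecast users | Share of 20,325 |
|---|---|---|
| ICD-9 (Italy 2,728 + Spain 646) | 3,374 | 16.6% |
| ICD-10 (Germany) | 3,871 | 19.0% |
| Read (UK) | 2,723 | 13.4% |
| Thesaurus (France 9,246 + Belgium 1,111) | 10,357 | 51.0% |

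The direct ICD-9 against ICD-10 contrast concerns the first two lines. Read and thesaurus counts depend on a mapping, and Appendix 3 does not say which of its two unequal columns that mapping should follow.

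**5. Which results are reached.**

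- *Separate renal-failure count:* directly, since it has no other source.
- *Moderate and severe counts:* defined by laboratory value, so unchanged unless codes complement missing values under section 3.3.2.
- *Pooled renal subgroup and off-label flag:* moderate, severe and failure all qualify, so a stage 3 patient with a qualifying value is counted either way. The main change is through 585.x, which can bring in patients with mild or unstaged disease and no value in either band.

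**The case against.** The strongest reply is that nothing assigns the chronic, acute or unspecified rows to renal failure. Section 3.3.2 gives those rows another natural use, the code search that complements missing laboratory data, and stage 3 codes belong in such a search. On that reading the list is a general one and the mapping is only unstated. Section 3.3.1 also defers harmonisation to the SAP, which is not at hand. Section 1.1 further suggests that the ICD-9 against ICD-10 contrast may involve few patients: reimbursement was undetermined in Italy and Spain and limited to 2013 in Germany, while the UK uses Read codes.

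Part of this stands. The documents do not show which rows will be used, so a reader who infers that the renal-failure count will certainly be inflated goes further than the text allows. The rest does not clear the point. Table 3.4.1-1 names Appendix 3 as the source of the definition, and section 4.1 says the SAP elaborates on the protocol, with major modifications made by amendment. Harmonising across coding systems cannot supply an end-stage row that the source list lacks. If the other rows are left out, the dialysis row alone is too narrow.

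The stage meaning of N18.3 and the contents of 585.x come from the ICD classifications. The missing row and the mismatch between a wildcard and a three-code list can be seen in the protocol alone.

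**Conclusion.** The point holds in a limited form. As written, Appendix 3 cannot deliver the renal-failure category of Table 3.4.1-1, and its chronic row selects different patients under ICD-9 and ICD-10. The separate renal-failure count and its comparison between countries are unreliable. The rest of the study is not undermined. The direction of error depends on the rows chosen, and the size cannot be computed from the documents.

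Three stronger readings are tempting and not supported:

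- *A several-fold inflation of renal failure.* Dividing 1 by (1 minus the stage 3 share) gives about 3.3 at 70% and 10 at 90%. Those shares are assumed, the formula still counts stage 4 as failure, and it presumes that the chronic row is used.
- *A large share of patients lost from moderate and severe.* Table 3.3.2-3 gives eGFR coverage of 79% (UK), 52% (Germany), 50% (Italy), 30% (Spain), 20% (France) and 9% (Belgium), so 21% to 91% lack a value. These are all T2DM patients in one year, before the two-year extraction and code search of section 3.3.2. They are neither dapagliflozin users nor coded kidney patients who are lost.
- *Wrong dialysis and transplant codes.* The protocol does not explain what these entries record, so they call for a check and are not a demonstrated error.

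**What to change.** In Appendix 3 and the renal rows of Table 3.4.1-1:

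1. Add a separate end-stage row and state which rows define renal failure.
2. Make the ICD-9 and ICD-10 entries equivalent, and stage-specific where a database's codes carry stage. Take stage 3 and stage 4 codes out of renal failure and align them with the moderate and severe bands.
3. Report acute, unspecified and unstaged codes separately.
4. Check that the dialysis and transplant entries identify patients who are on dialysis or have a transplant.
5. Beside the laboratory-only definition, show moderate and severe impairment by laboratory value or stage code as a sensitivity analysis. Section 3.3.2 already allows the code search. Without this step, a coded stage 3 or 4 patient with no laboratory value would fall outside every category once step 2 is made.

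The cost is one appendix table, three definition rows and one extra tabulation, with no new data collection. Stage codes are less exact than laboratory values, which is why both versions should be shown. Some databases may not record stage, and there the unstaged group should be reported as such. The change should be made before the first data extraction.
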